## **2. OBJECTIVES END ENDPOINT**

### ***2.1. OBJECTIF ET CRITERE D'EVALUATION PRINCIPAL***

#### **2.1.1. Primary objective**

The main objective of the study is to show that follow-up via the Moovcare web-application could make it possible to better identify the significant complications occurring between two systematic follow-up consultations with the specialist in patients followed for high-risk lymphoma. relapse than with standard follow-up. The evaluation of the main objective will be carried out over 6 months of follow-up.

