### 5.3. SCHEDULE OF THE STUDY

*For patients randomized to the “standard” arm:*

	Baseline	M3	M6	M9	M12	M15	M18	M21	M24
Eligibility criteria	X								
Study presentation / Written inform consent	X								
Cancer history	X								
Physical exam (PS, weight)	X (- 15 days)	X	X	X	X	X	X	X	X
Biology report (parameters at the discretion of the investigator)		X	X	X	X	X	X	X	X
Initial Symptom score	x								
Imaging assessment	X (- 4 weeks)		X		X		X		X
Quality of life questionnaires	X	X	X	X	X				

*For patients randomized to the “web-application follow up” arm:*

	Inclusion	M3	M6	M9	M12	M15	M18	M21	M24
Eligibility criteria	X								
Study presentation / Written inform consent	X								
Cancer history	X								
Physical exam (PS, weight)	X (- 15 days)	X	X	X	X	X	X	X	X
Biology report (parameters at the discretion of the investigator)		X	X	X	X	X	X	X	X
Initial Symptom score	x								
Self assessment	Every 14 days maximum for patients included in the “web application follow-up” arm								
Imaging assessment	X (- 4 weeks)	In the event of a Moovcare alert or clinical call point							
Satisfaction questionnaire			X						
Quality of life questionnaires	X	X	X	X	X				

CONFIDENTIAL

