### **6.2.1. Sample size determination**

The main objective of the study is to show that follow-up via the SENTINEL Lymphoma web-application could make it possible to better identify the significant complications occurring between two systematic follow-up consultations with the specialist in patients followed for high-risk lymphoma. relapse than with standard follow-up. The evaluation of the main objective will be carried out over 6 months of follow-up.

This study is based on a pooled triangle test analysis (24, 25, 26). Two groups will be composed, one will be monitored via the web-application, the other will be monitored in a standard way (consultation and imaging).

A 1: 1 randomization will assign the treatment group to the patient. Stratification on center, autologous transplant, PS, relapse and lymphoma type will be performed to ensure the comparability of our two populations at inclusion.

This sequential method will make it possible to evaluate during recruitment the diagnostic efficiency of significant complications outside systematic consultations while controlling the power (risk of accepting our null hypothesis wrongly) and the type I error (risk of rejecting our wrongly null hypothesis). This design allows us to consider stopping the trial as soon as the information gathered is sufficient to conclude. We will be able to conclude that the web-application is diagnostic efficiently or, on the contrary, that it is lacking in interest.

We set the risk of the first species alpha at 5%, the potency at 90%, we envisage that monitoring via the web-application allows us to identify significant complications between two systematic follow-ups in 90% of patients (i.e. 10% of patient presenting an event not identified early) against 60% (i.e. 40% of patient presenting an event not identified early) in the group followed in a standard way (i.e. a difference of 30%).

The early unidentified event is defined:

- in the web application follow up group by the absence of an alert in the following cases:
  - emergency hospitalization,
  - a medical consultation without follow-up with medical prescription (imaging / drug prescription)
  - a significant event at the classic follow-up consultation (very degraded PS, antibiotic therapy, supportive care with consultation, pulmonary embolism, sepsis, severe depression, etc.)
  
- – in the standard group in the following cases:

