  - emergency hospitalization, without medical consultation justifying this hospitalization,
  - a significant event at the classic follow-up consultation (very degraded PS, antibiotic therapy, supportive care with consultation, pulmonary embolism, sepsis, severe depression, etc.).

The events diagnosed during the follow-up consultation will be reviewed, in the form of a list (pooled data from the web-application follow-up and standard groups), by the coordinator, who will rule on the significance of the event.

- The hypotheses are written:

H0: The proportion of patients without an undiagnosed event outside the systematic consultation (follow-up visit and systematic imaging) is not different between the two groups.

H1: The proportion of patients without an undiagnosed event excluding systematic consultation (follow-up visit and systematic imaging) is higher with the web-application (by 30%) compared to standard follow-up (90% against 60%).

With 2 scheduled analyzes, it is necessary to include a maximum of 40 patients per group. The analyzes will be carried out every 2x20 patients included (20 in the control group and 20 in the group followed by web-application)

As the inclusions progress, two statistics will be calculated, one reflecting the efficiency and the other the amount of information accumulated. The whole will make it possible to draw a decisional graph, leaving the area thus drawn a conclusion will be possible. If we find ourselves above the zone we will conclude that H0 has been rejected, if we find ourselves below the zone we will conclude with an acceptance of H0 and therefore ineffective monitoring via the web-application.

CONFIDENTIAL

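### Only the standard arm has a systematic scan at M6, and the plan does not say whether findings seen on that scan alone count as primary failures

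*Combined protocol and SAP*

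**What the plan says.** **Window.** Section 2.1.1: "The evaluation of the main objective will be carried out over 6 months of follow-up". No visit window or cut-off says whether findings of the M6 scan fall inside it.

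**Imaging.** Sections 5.2 and 5.3 schedule systematic imaging at M6, M12, M18 and M24 in the standard arm. In the web-application arm, imaging after baseline is done only "In the event of a Moovcare alert or clinical call point". Clinical examination and biology are scheduled at M3 and M6 in both arms.

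**Hypotheses.** In section 6.2.1 (Sample size determination), H0 concerns patients without an undiagnosed event "outside the systematic consultation (follow-up visit and systematic imaging", the bracket being the plan's gloss on what is systematic. H1 repeats the gloss.

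**Failure definition.** The same section lists the failures by arm. Both lists contain a significant event found at the ordinary follow-up visit (in the web arm, if there was no alert). The clinical examples are open-ended and name neither relapse nor an imaging finding. An unscheduled consultation leading to a prescription, without an alert, is on the web-arm list only. The coordinator rules on the significance of visit-diagnosed events from a list pooled over arms.

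**Design.** "We set the risk of the first species alpha at 5%, the potency at 90" per cent; "With 2 scheduled analyzes, it is necessary to include a maximum of 40 patients per group".

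**The concern.** The primary comparison is a difference in failure proportions, so both arms need the same chance of having a failure found. At M6 a standard-arm patient has a visit and a scan, and a web-arm patient has a visit. A silent event visible only on imaging can be found in the first patient. It has no scheduled route to detection in the second, who scores as a success.

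If such findings count, the standard arm collects failures that reflect how hard one looked and not how well complications were picked up between visits. This would push the result towards the application even if it had no effect. Review of a pooled list does not solve this: it can strike events off, but it cannot add events that were never looked for.

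**Working it through.** **1. Do the documents make a scan-only finding a failure?** They neither say so nor exclude it.
- *For counting:* H0 and H1 place systematic imaging inside systematic follow-up; the list of significant events is open-ended; pulmonary embolism, which a scan can show, is one of its examples; and the section on planned statistical methods describes the events of 2.1.2 with relapse set aside, which suggests that relapse may be among them.
- *Against counting:* section 2.1.2 and the failure lists name no relapse or imaging finding, and relapse has its own secondary endpoints in 2.2.2.

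**2. Reproduce the plan's sample size.** Inputs from section 6.2.1 are "in 90% of patients (i.e. 10% of patient presenting an event not identified early) against 60" per cent, alpha 5%, power 90% and 1:1 allocation. Sidedness is not stated: H0 says not different, while H1 says success "is higher with the web-application (by 30%) compared to standard follow-up (90% against 60" per cent.
- Fixed sample, two-sided: n = [1.96·√(2·0.75·0.25) + 1.2816·√(0.6·0.4 + 0.9·0.1)]² / 0.3² = (1.2003 + 0.7362)² / 0.09 = 41.7, so 42 per arm.
- Two-look triangular test, one-sided 2.5%, log odds ratio ln 6 = 1.792: intercept a = 2.765, slope c = 0.5417. The boundaries meet where cV + 0.583·√(V/2) = a, so V = 3.65. With V = n·0.75·0.25/2, n = 39 per arm.

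Both are close to the stated 40. The one-sided 5% triangular version gives 33, so one-sided 2.5% boundaries are used below. They are a reconstruction, since the plan prints none.

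**3. Yield of the scan, x.** The only imaging-yield percentage from a cited study is 1.7% of patients (section 1.2), in a diffuse large B-cell cohort and for routine surveillance as a whole, not for one M6 scan. Section 1.4 says less than 2%. For this high-risk population no figure is given; 5% is an assumption.
- x = 1.7%: 40 × 0.017 = 0.68 patients with a scan-only finding.
- x = 5%: 40 × 0.05 = 2 patients.

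**4. Type I error with no true effect.** Exact enumeration of the two-look design (20 + 20 per arm), true success 60% in both arms. Two ways of applying x bracket the answer:
- x applies only to otherwise event-free patients: standard-arm success 0.6(1 − x);
- worst case, every scan-only finding is an extra failure: 0.6 − x.

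| x | 0.6(1 − x) | Error | 0.6 − x | Error |
|---|---|---|---|---|
| 0 | 0.600 | 2.7% | 0.600 | 2.7% |
| 1.7% | 0.590 | 3.2% | 0.583 | 3.6% |
| 5% (assumed) | 0.570 | 4.5% | 0.550 | 6.1% |

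The result depends on the set-up. With one-sided 5% boundaries and the first method, the error goes from 4.8% to 5.6% (x = 1.7%) and 7.4% (x = 5%). With true success of 90% in both arms and 2.5% boundaries, simulation gives 0.9%, 1.8% and 5.1%.

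**5. Power if scan-only failures are not counted.** If the planned 60% included them, standard-arm success becomes 0.6 + x. Fixed-sample two-sided power at 40 per arm is Φ{[d − 1.96·√(2p̄q̄/40)] / √[(p₁q₁ + p₂q₂)/40]}, with p₂ = 0.9 and d the difference:
- p₁ = 0.600: (0.300 − 0.1898)/0.0908 = 1.214, power 88.8%;
- p₁ = 0.617: (0.283 − 0.1876)/0.0903 = 1.057, power 85.5% (46 per arm for 90%);
- p₁ = 0.650: (0.250 − 0.1830)/0.0891 = 0.752, power 77.4% (57 per arm for 90%).

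Under the reconstructed triangular design the same sequence is about 86.7%, 83.4% and 75.0%. If the 60% did not include scan-only failures, nothing changes.

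**The case against.** A reader might infer that the hypotheses turn every scan-only event into a failure. The documents do not support this: the gloss in H0 says what systematic follow-up consists of and adds no event type, and M6 is the edge of the window. What stands is a gap in the definition.

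A reader might also infer that the primary endpoint as a whole is biased towards the application. That is not established either. An unscheduled consultation with a prescription and no alert is a failure in the web arm only, which works against the application. The documents give no rate for it, so the two can be neither netted off nor assumed to cancel.

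The sponsor can fairly say that imaging is part of the strategy under comparison. That justifies different scanning by arm. It does not make a failure that only one arm can show a measure of better identification between visits, which is the stated objective.

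Finally, the effect is small at the protocol's own figure. This is accepted.

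**Conclusion.** The point holds as a gap in ascertainment. The plan does not exclude findings made solely by the standard-arm M6 scan from the primary endpoint, and if counted they can arise in that arm only. This component favours the application; the net direction across the whole failure definition is unknown.

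At the documents' 1.7% the size is minor: under one patient in 40, and a rise in one-sided error of about 0.5 to 0.9 percentage points. It becomes material at a yield of about 5% or more, which is an assumption for this population. The error rates rest on reconstructed one-sided 2.5% triangular boundaries and 60% success in both arms. The change is worth making because it is cheap and alters no care, not because the expected distortion is large.

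**What to change.** In sections 2.1.2 and 6.2.1 (Sample size determination), state that an event at a follow-up visit is a primary failure only if found by means scheduled in both arms: history, examination or biology at M3 and M6. Add one e-CRF field for how each event was found. Report events found solely by the systematic M6 scan separately, with a sensitivity analysis that includes them. Leave the imaging schedule as it is.

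The cost is one definition sentence, one data field and the possible loss of power in step 5. The sponsor should therefore state whether the planned 60% included scan-only failures. One limit remains: the biology parameters are at the investigator's discretion, so the rule equalises scheduled opportunity but does not guarantee identical testing.

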### **1.3. MOOVECARE TOOL FOR LYMPHOMA RELAPSE DETECTION**

We have developed a score based on the dynamics and the combination of clinical and biological signs to alert the doctor of a possible recurrence of lymphoma

[figure not shown]
The considered clinical symptoms will be self-assessed (presence / absence or no problem / slight problem / medium problem / significant problem) by patients every 1 to 2 weeks, sent by their Smartphone or computer via the Internet, and will be analyzed by software that determines whether or not a relapse or significant complication is likely. The referring doctor will thus be alerted early and will summon the patient early for a check-up.

A similar application has been developed to detect relapse of lung cancer early (20, 21). The prospective study of this application showed interesting results in these patients with 100% sensitivity, 89% specificity, 81% PPV and 100% NPV with 11 symptoms studied. In the initial study to establish a detection algorithm based on only 6 symptoms, a NPV of 93% was already noted (20). In addition, relapses were detected on average 5 weeks before the scheduled date of the follow-up assessment (images every 3 months) (21).

An analysis of overall survival (monocentric and non-randomized) in our center also suggests a gain in survival of nearly 24% at 1 year ( $p = 0.02$ ) (22). This gain in survival is most likely related to the early initiation of salvage treatment and supportive care.

In the follow-up of the patients, it appeared that the algorithm was more sensitive if the patients were not very symptomatic at inclusion and had an initial score of less than 7 (by adding the scores of 0 to 3 for the symptoms concerning cough, dyspnea, pain, anorexia and asthenia: no problem = 0, mild problem = 1, medium problem = 2, significant problem = 3). A phase 3 study comparing this computerized surveillance with surveillance according to the usual method is in progress.

The results of the interim study suggest a favorable trend in overall survival in user and compliant patients (use at least once a week): 62% in the standard arm versus 87% in the SENTINEL arm:  $p(\text{logrank})=0,038$  (23).

Results of the interim analysis of the phase 3 study  
Per-protocol analysis of overall survival ( $p=0,038$ ).

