#### **5.1.1. Clinical assessment**

It includes a complete clinical examination (within 2 weeks prior to inclusion) with:

- the history of the disease,
- the evaluation of weight and PS,
- the calculation of the initial score,
- completion of the QLQ-C30 and PhQ-9 quality of life questionnaires.

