### 6.2.3 Randomization

Randomization 1: 1 will be performed following minimization with stratification on the center, autologous transplant, PS, relapse and type of lymphoma. Randomization will be carried out by the investigator directly via the electronic CRF developed with ENNOV Clinical® software (Cenon, France).

Randomization will only be possible after the main data has been recorded on the e-CRF (date of signature of consent, stratification criteria, inclusion and non-inclusion criteria).

The patient's home group will be instantly displayed on the e-CRF after performing the randomization. A randomization confirmation email will also be sent to the investigator.

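### The initial symptom score is recorded in every patient but used neither in the minimisation nor in the primary triangular test; stratifying the test on it is a cheap, minor efficiency gain

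*Combined protocol and SAP*

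**What the plan says.** Baseline work-up in both arms includes "the calculation of the initial score" (section 5.1.1), and both schedules in section 5.3 list it. Inclusion criterion 5 (section 4.1) admits only patients scoring 5 or less.

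Section 6.2.3 allocates patients 1:1 by "minimization with stratification on the center, autologous transplant, PS, relapse and type of lymphoma". The symptom score is not in that list.

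Section 6.2.1 (Sample size determination) plans a triangular test with two analyses, after 20 and then 40 patients per group, in which "two statistics will be calculated, one reflecting the efficiency and the other the amount of information accumulated". No covariate is named for either statistic, not even the minimisation factors.

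Section 1.3, describing experience with the lung-cancer application, reports that "the algorithm was more sensitive if the patients were not very symptomatic at inclusion" with an initial score below 7. That score adds five symptoms, each rated 0 to 3.

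**The concern.** The score is already on file before randomisation, and the sponsor thought it important enough to restrict entry on it. Several of the failures counted in the primary endpoint (a marked fall in performance status, severe depression, referral for supportive care, emergency admission) could well be commoner in patients who start with more symptoms, whichever arm they are in. If so, a test that ignores the score gives away some power. It also lets a chance imbalance in baseline symptoms pass straight into the decision graph. The trial is small and may stop after 20 patients per arm, where such imbalances are most common.

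What is at stake is a few points of power and some robustness at the first analysis. The validity of the test and the planned size are not in question.

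**Working it through.** **1. Reproducing 40 per group.** Section 6.2.1 gives the inputs: "We set the risk of the first species alpha at 5%, the potency at 90" per cent, and success of 90% with the application against 60% with standard follow-up. Sidedness is not stated. Using Whitehead's triangular test on the log odds ratio with 0.025 in the upper tail:

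- θ = log[(0.9/0.1)/(0.6/0.4)] = log 6 = 1.792
- θ′ = 2 × 1.960/(1.960 + 1.2816) × 1.792 = 2.167
- a = (2/θ′) log(1/0.05) = 2.77; c = θ′/4 = 0.54
- With two looks, solve a − 0.583√(V/2) − cV = 0, giving V = 3.65
- Patients per group = 2V/(0.75 × 0.25) = 38.9, so 39

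This is within one patient of the stated 40. With a one-sided 5% level the result is 34. The figure therefore reproduces without any covariate, and nothing below changes it.

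**2. Chance imbalance.** Assume simple randomisation and a score split 50/50 into low and high. A difference between arms of 20 percentage points or more in the high-score share then occurs in about 27% of trials at 20 per arm and 9% at 40 per arm. Type I error of the unadjusted test at 40 per arm (single look) stays at 5.2–5.4%, because chance imbalance is already part of that error.

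**3. Possible gain, by formula.** The documents give no correlation ρ between score and outcome, so a range is assumed. Adjustment cuts variance by ρ², and from 90% power

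power = Φ[(1.96 + 1.2816)/√(1 − ρ²) − 1.96].

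| ρ (assumed) | Variance cut | Power |
|---|---|---|
| 0.2 | 4% | 91.1% |
| 0.3 | 9% | 92.5% |
| 0.4 | 16% | 94.3% |
| 0.5 | 25% | 96.3% |

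**4. Possible gain, single-look simulation.** 40 per arm, 40% against 10% failure, two-sided 5%, score assumed uniform on 0–5, three bands, 20,000 trials:

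| Logistic slope per point (assumed) | Link in both arms: unadjusted → stratified | Link in web arm only |
|---|---|---|
| 0 | 90.3% → 90.0% | – |
| 0.3 | 89.9% → 90.6% | 90.3% → 90.1% |
| 0.5 | 90.4% → 92.6% | 90.2% → 90.0% |
| 0.8 | 90.1% → 94.8% | 90.2% → 90.3% |

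In the both-arms case, slopes of 0.5 and 0.8 correspond to correlations of 0.38 and 0.54 in the control arm and 0.24 and 0.34 in the web arm. A separate run with a two-level score and a Mantel-Haenszel test lost about 0.5 points when the score was unrelated to outcome (90.2% to 89.7%). It gained up to about 3 points when the score acted in both arms (90.2% to 93.7%).

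**5. In the planned two-look design.** Looks at 20 and 40 per arm, boundaries as in step 1, two fixed score bands. In each band k, with n₁ and n₀ patients, S failures among N = n₁ + n₀, and f₁ failures in the web arm:

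- Z = Σₖ (n₁S/N − f₁)
- V = Σₖ n₁n₀S(N − S)/N³

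The unadjusted test has power of about 87%, with about 2.4% of trials crossing no boundary. With two bands:

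- Type I error (upper tail) was 2.1–3.2%, against 2.6–3.0% unadjusted.
- Power did not fall when the score was unrelated to outcome. It rose by about 1, 3 and 5 points at slopes of 0.3, 0.5 and 0.8 in both arms, and by 0 to 1 point when the link was in the web arm only.
- Trials crossing no boundary by 80 patients rose from about 2.5% to 3–5% under H1, and from about 1% to at most 6.5% under H0.

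**6. Why two bands and not three.** At 20 per arm about 20 × 0.4 + 20 × 0.1 = 10 failures are expected in all. Three bands with the simple variance gave type I error of 5.7–5.9% there (two-sided), against 4.6–4.9% unadjusted. Mean information at that look fell from 1.83 to 1.65.

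**The case against.** The strongest objection is to the premise. A reader might infer from section 1.3 that the protocol itself says the score predicts how well events are detected in this trial. It does not. The remark concerns the lung-cancer tool and a threshold of 7, and inclusion criterion 5 puts every patient on the favourable side of it. The sponsor has already acted on it by restricting entry. No passage reports a gradient between 0 and 5, or any link for the lymphoma score. This stands in full.

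A second objection also stands. Sensitivity of the algorithm can matter only in the arm that uses it. That is effect modification, not prognosis, and in that case step 5 shows almost no gain. The larger gains need a link in both arms, which is clinically plausible but undocumented.

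Third, randomisation makes the unadjusted test valid, so leaving the score out is no error. This is agreed.

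Fourth, one may doubt that a stratified statistic behaves well with the planned boundaries and 80 patients. Step 5 answers this for two fixed bands: type I error stays close to 2.5% and the loss of information is modest. The doubt is fair for three bands, or for bands redrawn after seeing the data.

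Finally, the plan does not say whether the minimisation factors enter the test, and performance status may carry part of the same information. That should be stated too, but it is no reason to leave the score unused.

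**Conclusion.** The score is measured in every patient, is not a minimisation factor and is not used in the primary test. Using it would be a small improvement: about 0 points of power if it is unrelated to outcome or acts almost only through the web arm, and about 1 to 5 points if it predicts outcome in both arms. These figures rest on assumed slopes, a score assumed uniform on 0–5, simple randomisation in place of minimisation, and a 0.025 upper-tail boundary.

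It would be wrong to conclude that the comparison is biased, that type I error is materially inflated, or that 40 per group is too few on this account. The documents and the calculations support none of these. This is a minor efficiency improvement, not a validity defect.

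**What to change.** In section 6.2.1 (Sample size determination):

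- Define the efficiency and information statistics as sums over two bands of the initial symptom score. Fix the cut point before the first analysis and do not redraw it on the data.
- Keep the triangular boundaries, and confirm type I error by simulation at 20 and 40 per arm with the exact variance formula to be used.
- Report the unadjusted result as a sensitivity analysis.
- State whether the minimisation factors enter the primary test.

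The cost is some plan wording, a few lines of code and one simulation, with no new data and no change in sample size. The downside is slightly less accumulated information, so a few more trials would reach 80 patients without crossing a boundary. If the score proves unrelated to outcome, the simulated loss of power is at most about half a point.

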## **6.2. STATISTICS**

### **6.2.1. Description of planned statistical methods**

This study should allow us to evaluate the functioning of the application in a follow-up context in patients with lymphoma at high risk of relapse.

The patient sample for this analysis will consist of all patients, included in the study and meeting all the eligibility criteria described in Chapter 4, who have signed a consent.

The initial characteristics of the analysis population (demographic data, disease, previous and concomitant treatments, prognostic factors, etc.) and all the evaluation criteria described in paragraph 2 will be presented globally

For the qualitative variables, we will present the number as well as the percentage. For quantitative variables, we will present the median or the mean plus or minus the standard deviation depending on the normality of the variable, the minimums and maximums will also be indicated.

Events, as defined in chapter 2.1.2. (apart from relapse) will be described in terms of frequency by etiological type (HLT or HLG T according to the MedDRA classification) and by severity according to NCI CTCAE v4.02.

For the analysis of the censored data (overall survival and other timeframes of events), the survival curves will be plotted according to the Kaplan-Meier estimates, the medians of survival will be presented as well as their 95% confidence intervals.

For performing multivariate survival analyzes, the semi-parametric Cox model will be used to calculate the odds ratios which will be presented with their 95% confidence interval.

The sensitivity of the application to detect a relapse and / or significant complications will be calculated.

Quality of life scores will be calculated according to EORTC guidelines for the QLQ-C30. The quality of life will be described at each measurement time and compared to inclusion and then studied longitudinally using mixed analysis of variance models for repeated measures.

PHQ9 scores will be calculated according to the recommendations, described at each measurement time and compared to inclusion. The classes proposed in the literature ( $\leq 4$ ; 5-14;  $> 14$ ) will be used to describe the state of depression of patients.

The analyzes will be carried out with SAS 9.3 software (SAS Institute Inc. Cary, NC, USA).

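### A lower-boundary exit is to be read as ineffective monitoring, although the design speaks only to a 30-point gain and no confidence interval for the primary difference is planned

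*Combined protocol and SAP*

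**What the plan says.** The null hypothesis in section 6.2.1 (Sample size determination) is that the proportion of patients without an undiagnosed event "is not different between the two groups". The alternative is that this proportion "is higher with the web-application (by 30%) compared to standard follow-up (90% against 60" per cent). Error rates are fixed in one sentence: "We set the risk of the first species alpha at 5%, the potency at 90" per cent. Analyses follow every 20 + 20 patients, with at most two analyses and 40 patients per group.

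The conclusions are binary. An exit above the zone rejects H0. After an exit below it, "we will conclude with an acceptance of H0 and therefore ineffective monitoring via the web-application". The same section also puts it this way: "We will be able to conclude that the web-application is diagnostic efficiently or, on the contrary, that it is lacking in interest".

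For reporting, section 6.2.1 (Description of planned statistical methods) says: "For the qualitative variables, we will present the number as well as the percentage". The 95% intervals it names are for median survival and for the Cox model. None is planned for the between-arm difference in the primary proportion. No smallest worthwhile gain is defined.

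**The concern.** H0 (no gain) and H1 (a 30-point gain) leave everything in between unassigned. The lower boundary is calibrated so that a true 30-point gain has only about a 10% risk of ending below it. It carries no such assurance for gains of 10, 15 or 20 points. Accepting H0 is ordinary language for a triangular test and is not the problem. The problem is the further step from acceptance to ineffectiveness.

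At stake is a prespecified, publishable statement that the application does not work. It would rest on 40 to 80 patients, with no planned interval to show which gains remain compatible with the data.

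**Working it through.** **Inputs from section 6.2.1 (Sample size determination).** Alpha 5%, power 90%; success rates 90% and 60%; 1:1 allocation; looks at 20 and 40 per arm.

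**Assumptions, because the plan does not state them.** The standard triangular boundaries, with V computed from the pooled data at each look; alpha read as 2.5% per side or as 5% one-sided; control rate 60%; no dropout.

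**1. Reproducing the planned size (2.5% per side).**
- θ = ln[(0.9/0.1)/(0.6/0.4)] = ln 6 = 1.79.
- Rescaled for unequal α and β: θ* = 2 × 1.96 × 1.79/(1.96 + 1.28) = 2.17.
- a = (2/θ*) ln(1/(2α)) = (2/2.17) ln 20 = 2.765; c = θ*/4 = 0.542.
- Upper boundary Z = a + cV; lower boundary Z = −a + 3cV. Each is moved inward by 0.583√(increment of V).
- They meet where V = (a − 0.583√(V/2))/c, so V = 3.65.
- N = 4V/[p̄(1 − p̄)] = 4 × 3.65/(0.75 × 0.25) = 77.9, or 39 per group. In blocks of 20 this is the stated 40.

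The same steps at 5% one-sided give N = 66, so 2.5% per side fits the plan better. Both are shown below.

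**2. Probability of ending below the zone.** Exact binomial enumeration over both looks, with Z = (difference in successes)/2 and V = 2m·p̄(1 − p̄)/4 for m per arm:

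| True gain over 60% | 2.5% per side | 5% one-sided |
|---|---|---|
| 0 points | 97% | 95% |
| 15 points | 74% | 68% |
| 20 points | 55% | 49% |
| 25 points | 33% | 28% |
| 30 points | 13% | 11% |

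The handling of the second-look correction moves these by about one point. At a true gain of 20 points, 34% of all trials (41% at 5% one-sided) would receive the verdict at the first look, on 20 patients per arm.

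**3. What such a result looks like.**
- First look, 14/20 against 12/20: +10 points, ordinary 95% CI −19 to +39. With p̄ = 0.65, V = 2.275 and Z = 1. The lower boundary (2.5% per side) is −2.765 + 3 × 0.542 × 2.275 + 0.583√2.275 = 1.81, so the trial stops and is reported as ineffective.
- Final look, 31/40 against 24/40: +17.5 points. SE = √(0.775 × 0.225/40 + 0.6 × 0.4/40) = 0.102, so the ordinary 95% CI is −2.4 to +37.4. This falls short of the upper boundary and is also reported as ineffective.

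Both intervals contain the full 30 points as well as zero.

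**4. How much is power.** In a fixed design with 40 per arm and two-sided 5%, at 80% against 60%: SE under H0 = √(2 × 0.7 × 0.3/40) = 0.1025; SE under H1 = √((0.16 + 0.24)/40) = 0.100. The chance of not rejecting is 1 − Φ[(0.20 − 1.96 × 0.1025)/0.100] = 50%. At 85% against 60% it is 28%. The triangular test gives 55% and 33%, so most of the probability is sample size.

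**5. The estimate after an early efficacy stop.** At a true 30 points and 2.5% per side, 54% of trials stop for efficacy at the first look, with a mean raw difference of about 39 points (about 36 at 5% one-sided). Over all trials the mean is 31.9, a bias of about 2 points. Ordinary 95% intervals cover in about 92 to 94% of trials.

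**The case against.** The sponsor powered for 30 points, and low power for smaller gains follows from that choice. That stands: as step 4 shows, the percentages should not be presented as damage done by the stopping rule. It does not rescue the wording. A trial with roughly even odds of missing a 20-point gain cannot declare the absence of effect when it misses.

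It is also fair that no smallest worthwhile gain is defined, so a reader cannot infer that 15 or 20 points would be clinically useful. The point needs only that such gains differ from none.

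A stronger reading is tempting on the positive side: that an early stop would publish a badly inflated effect, and that a median-unbiased estimate would cure it. Neither half is well supported. The 39-point mean belongs to one subset of trials under one reading of alpha, and the overall bias is about 2 points. Under stagewise ordering, a trial stopped at the first look is ranked only against more extreme first-look results. Its median-unbiased estimate is therefore essentially the raw one, and the inflation remains.

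Nor are raw percentages the only planned output. The plan also calculates two sequential statistics and a decision graph. These support the decision, but no interval for the difference is derived from them. The references cited for the triangular test may cover estimation, but the plan adopts no method from them.

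**Conclusion.** The concern holds for the interpretation of a lower exit and for the missing interval. As written, the rule would label the application ineffective in about 74%, 55% and 33% of trials at true gains of 15, 20 and 25 points (68%, 49% and 28% with 5% one-sided boundaries). These figures rest on the boundary form, sidedness, 60% control rate and absence of dropout assumed above, and mainly express the limited power of 40 per arm. The early-stop inflation is a secondary matter that calls for a caution in reporting. The documents do not support reading it as a serious overall bias. Nothing here calls the sample size or the boundaries into question.

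**What to change.** In section 6.2.1 (Sample size determination), change both statements of the negative conclusion so that an exit below the zone means: *a 30-point improvement is not supported; smaller gains are not excluded.*

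In section 6.2.1 (Description of planned statistical methods), add that the between-arm difference in the primary proportion will be reported with a 95% confidence interval that accounts for the sequential design. It should be given whichever boundary is crossed, and benefit should be interpreted from it. Add one sentence that, after an efficacy stop at the first look, the point estimate tends to overstate the effect and that a stagewise median-unbiased estimate does not remove this.

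The cost is a few sentences and one additional planned output. Sample size, boundaries, error rates and patient procedures do not change. The one real downside is a less categorical negative conclusion.
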